5.3.2.2.2 Pregnancy outcomes

Elective or therapeutic pregnancy terminations

Elective or therapeutic pregnancy terminations are defined as any induced or voluntary fetal loss during pregnancy. If available, data from pathologic examination of the abortus or fetus will be evaluated by the Adjudication Committee [see Section 10] for structural or chromosomal defects. The reason for elective or therapeutic termination will be collected. Elective versus therapeutic terminations will be summarized separately.

Spontaneous abortions

A spontaneous abortion is defined as loss of a fetus due to natural causes at < 20 weeks of gestation. If available, information from gross or pathologic examination of the abortus or fetus will be evaluated by the Adjudication Committee [see Section 10] for structural and chromosomal defects.

Fetal death or stillbirth

Fetal death or stillbirth refers to the death of a fetus prior to birth at or after 20 weeks of gestation. In the event of a stillbirth or fetal death, full pathology details will be requested and examined for structural or chromosomal defects. The final classification between fetal death / stillbirth and spontaneous abortion will be based on gestational age.

Live birth

A live birth refers to a complete expulsion or extraction from its mother of a surviving neonate.

Preterm birth

A live birth will be classified as preterm prior to 37 weeks of gestation according to the CDC definition [cdc.gov_a]. Preterm birth will be categorized as early preterm (< 34 weeks), late preterm (34–36 weeks), and early term (37–38 weeks).

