5.4.4.1 Metropolitan Atlanta Congenital Defects Program

The MACDP, a population-based tracking system for birth defects (established in 1967) in the US, currently captures approximately 35,000 births per year from 3 metropolitan counties in the Atlanta area [CDC 2021]. MACDP has monitored trends in birth defects rates and has served as a case registry for descriptive, risk factor, and prognostic studies of birth defects. Since 1998, MACDP surveillance has required that any signs or symptoms of a defect in the child be reported before their sixth birthday. In a 2007 report, the MACDP presented data on the prevalence and descriptive characteristics of birth defects, including 67 individual defects, in metropolitan Atlanta, Georgia from 1968 to 2003 [Correa 2007].

Major structural or genetic birth defects affected approximately 3% of births in the US [CDC 2008]. The prevalence estimates of stillbirth in 2006 and 2008 using MACDP data were 8.0 (95% CI: 7.3–8.7) and 7.6 (95% CI: 6.9–8.4) per 1000 live births plus stillbirths [Duke 2014].

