Categorical distributions available in the MACDP will be summarized using the same categories among the QUVIVIQ-exposed pregnancies. Indirect standardization methods will be applied for categorical distributions of maternal age, gestational age, and race/ethnicity. Indirect standardization involves calculating the observed number of events (i.e., major congenital malformations) and applying the maternal age, gestational age, and race/ethnicity distributions from the reference population (i.e., MACDP and EUROCAT) to calculate the expected number of major congenital malformations. The ratio of the observed number of major congenital malformations to the expected number of major congenital malformations is referred to as the standardized prevalence ratio.

Adjusted prevalence can be calculated by multiplying the standardized prevalence ratio by the crude congenital malformation rate.

It is important to emphasize that any external comparator data source and women enrolled in this study are 2 distinctly different datasets, thus "external adjustment methods" for inference comparisons are limited.

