5.9.2 External validity of study design

To ensure internal comparability where feasible, Cohort B will be recruited from the same clinical centers through HCP awareness and use the same recruitment strategies [see Section 5.4.5] as Cohort A. However, the study population may not be reflective of the broader source population of pregnant women with insomnia. Participation in the study is completely voluntary which may lead to a particular type of patient group, such as women with severe insomnia who have taken medication(s) "at-risk" due to the severity of their condition. Additionally, there are a wide range of treatments for insomnia such that the distributions of insomnia treatment exposures in the study may not be reflective of the treatment distributions in the source population, which could impact generalizability.

As there are no patient-level data available for the external comparator cohorts, there may be underling differences between populations that are not detectable. However, reported categorical distributions of maternal age groups, race/ethnicity, or gestational age at birth may be available for comparison to ensure baseline similarities to the registry population and external adjustment methods (i.e., direct or indirect adjustment with a standard population) may be used.

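### The external comparison is called indirect standardization but applies the reference population's distributions, so the ratio is not adjusted as labelled; it also standardizes on gestational age at birth

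*Protocol*

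**What the plan says.** Protocol section 5.7.4.3, under the external comparator analysis, states: "Indirect standardization methods will be applied for categorical distributions of maternal age, gestational age, and race/ethnicity". The expected count comes from "applying the maternal age, gestational age, and race/ethnicity distributions from the reference population", the reference being MACDP and EUROCAT. Then: "The ratio of the observed number of major congenital malformations to the expected number of major congenital malformations is referred to as the standardized prevalence" (this quotient is abbreviated SPR below). Finally: "Adjusted prevalence can be calculated by multiplying the standardized prevalence ratio by the crude congenital malformation rate". The text does not say whether that crude rate belongs to the reference population or to Cohort A.

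No section says that reference prevalences by stratum are applied to Cohort A's counts.

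Section 5.9.2 shows which gestational age is meant: "reported categorical distributions of maternal age groups, race/ethnicity, or gestational age at birth may be available for comparison to ensure baseline similarities". It adds that direct or indirect adjustment may be used. Section 5.3.2.2.2 makes preterm birth a registry outcome: "A live birth will be classified as preterm prior to 37 weeks of gestation according to the CDC definition".

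On ascertainment, section 5.4.4.1 reports that MACDP has since 1998 required that "any signs or symptoms of a defect in the child be reported before their sixth birthday", and its approximately 3% figure covers structural or genetic defects. The registry's primary outcome counts malformations reported up to 1 year of age (section 5.7.1.3). Table 5, Subgroup 2, removes women with a known aneuploid or genetic finding from primary and secondary analyses.

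**The concern.** The method named and the method described differ. Indirect standardization asks how many cases Cohort A would have had if each of its strata carried the reference prevalence. That needs the reference's stratum prevalences and Cohort A's stratum sizes. Weighting by the reference population's distribution belongs to direct standardization and does not yield the expected count that an SPR needs.

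A programmer who follows the section would report a ratio labelled as standardized that is not adjusted for maternal age or race/ethnicity.

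Two further statements compound this. The unspecified crude rate can change the adjusted prevalence substantially. Gestational age at birth is determined after exposure and may respond both to exposure and to malformation, so standardizing on it can remove part of an effect.

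**Working it through.** **Inputs from the Protocol.** N = 102 Cohort A pregnancy outcomes and 3.15% expected prevalence (section 5.5.1), reference prevalence about 3% (section 5.4.4.1), premature birth 11% (Table 4). The Protocol gives no SPR or expected count to reproduce. Stratum shares and stratum rates are assumptions, varied below.

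**Notation.** In stratum i, n_i is the Cohort A count, w_i the reference share, R_i the reference prevalence and r_i the Cohort A prevalence. O is the observed count, O = Σ n_i r_i.

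**Three expected counts**
- Indirect standardization: E = Σ n_i R_i.
- Literal reading 1 (reference distribution, reference prevalences): E = N Σ w_i R_i = N × crude reference rate. O/E is the crude ratio.
- Literal reading 2 (reference distribution, Cohort A prevalences): E = N Σ w_i r_i. Both O and E use Cohort A's own prevalences, so O/E compares Cohort A with itself.

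**One worked mix.** Assume age-stratum prevalences of 3.0/2.8/4.0%, a reference mix of 25/57/18% and a Cohort A mix of 5/50/45%.
- Indirect: 102 × (0.030×0.05 + 0.028×0.50 + 0.040×0.45) = 102 × 0.0335 = 3.417.
- Reading 1: 102 × (0.030×0.25 + 0.028×0.57 + 0.040×0.18) = 102 × 0.03066 = 3.127.
- 3.417/3.127 = 1.093, so in this mix the literal ratio is 9% too high.

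**Range.** Two age strata, reference crude rate fixed at 3%. Entries are O/E under reading 1 when every Cohort A stratum has exactly the reference prevalence, so the correct value is 1.00.

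| Share aged 35+, reference / Cohort A | Older-to-younger rate ratio 1.25 | 1.5 | 2.0 |
|---|---|---|---|
| 15% / 35% | 1.048 | 1.093 | 1.174 |
| 15% / 50% | 1.084 | 1.163 | 1.304 |
| 20% / 10% | 0.976 | 0.955 | 0.917 |

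Reading 2 returns these same values even when every Cohort A stratum prevalence is doubled and the correct ratio is 2.00. The indirect formula returns 1.00 and 2.00 exactly in every cell.

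**Crude rate.** Take SPR = 2 and a 3% reference. Using the reference rate, 2 × 3% = 6%. Using Cohort A's own crude rate of 6%, 2 × 6% = 12%. Only the first is an adjusted prevalence.

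**Gestational age at birth.** Take a reference preterm share of 11%, a preterm-to-term malformation rate ratio k, and a true overall ratio of 2.0, so O = 2 × 102 × 0.03 = 6.12. The reference term rate is t = 0.03/(0.89 + 0.11k), and for Cohort A preterm share p, E = 102 × t × [(1−p) + pk].
- k = 2, p = 16.5%: t = 0.02703, E = 3.21, ratio 6.12/3.21 = 1.91.
- k = 5, p = 22%: t = 0.02083, E = 4.00, ratio 6.12/3.995 = 1.53.
- k = 3, p = 5.5% (half the reference share): t = 0.02459, E = 2.78, ratio 6.12/2.784 = 2.20.

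The ratio falls when Cohort A has more preterm births than the reference and rises when it has fewer.

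**The case against.** The strongest defence is loose wording. The section names the right method, forms observed over expected, and plans to summarize MACDP categories in the same way among exposed pregnancies, which would supply the stratum counts needed. The sponsor may well intend the correct calculation. That stands as a guess at intent, but the sentence defining the expected count still says something else, and section 5.9.2 leaves even the choice between direct and indirect adjustment open.

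The stakes are low, and this stands. Sections 5.4.4 and 5.7.4.4 make the external comparison descriptive, and section 5.7.4.3 itself calls inference from it limited. With about 3 cases (102 × 3.15% = 3.2), the exact Poisson 95% interval for a count of 3 is roughly 0.6 to 8.8, so a 9% shift lies far inside the noise.

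Three stronger inferences are not supported:
- That the formula and gestational age together make the registry look safe. The formula error can go either way, and in the worked mix it overstates the ratio. The gestational-age direction turns on a preterm share nobody yet knows.
- That 9% is the size of the error. It belongs to one set of assumed strata.
- That all genetic cases should be put into the registry numerator to match MACDP. That would bring back Table 5 Subgroup 2, whose results were known before enrollment, and with it the outcome-dependent enrollment that section 5.2 seeks to reduce.

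**Conclusion.** Wrong as written. The stated rule for the expected count does not perform indirect standardization, and under either literal reading the SPR is not adjusted for maternal age or race/ethnicity. Its size and direction depend on unknown strata: 0.92 to 1.30 in place of 1.00 over the assumed mixes. The crude rate in the adjusted-prevalence step must be the reference population's, which the text does not say.

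Standardizing on gestational age at birth is a separate fault. It can remove part of an effect, in a direction that cannot be stated in advance.

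The ascertainment difference is a matter of comparability, not of the formula. Later reporting and the inclusion of genetic defects in MACDP tend to lower the registry figure relative to the reference.

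The consequence is confined to a descriptive secondary analysis. The primary comparison of Cohort A with B1 and the sample size are untouched.

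**What to change.** Replace the description in section 5.7.4.3 with:
- Expected cases = sum over maternal age and race/ethnicity strata of (Cohort A pregnancies in the stratum × MACDP or EUROCAT prevalence in that stratum). If joint stratum prevalences are not published, use one variable at a time.
- SPR = observed/expected, with an exact Poisson 95% confidence interval.
- Adjusted prevalence = SPR × the reference population's crude prevalence.
- Gestational age at birth removed from the main SPR, or kept only as a sensitivity analysis. Section 5.9.2 should no longer present it as a baseline characteristic.

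Keep the Table 5 Subgroup 2 exclusion. Beside the SPR, report that MACDP counts defects reported before the sixth birthday and includes genetic defects, while the registry counts to 1 year and excludes some genetic cases, and state the likely direction.

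The cost is a wording change in the Protocol, carried into the SAP, with no new data collection in the registry. One thing must be confirmed first: that the reference sources publish prevalences by stratum and not only the distribution of births. The Protocol says only that aggregate data will be used, so this cannot be checked from it.

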5.7.4.4 Sensitivity and subgroup analyses

Sensitivity analyses will be performed on both Cohort A and Cohort B if sufficient sample size allows, including but not limited to that which is listed in Table 6.

Table 6 Sensitivity analysis subgroups and outcomes analyzed

Subgroup	Outcome analyzed
Women who have received any prenatal testing that provides knowledge of pregnancy outcome, regardless of findings	Major congenital malformations
Women who have received any prenatal testing that provides knowledge of pregnancy outcome before enrollment, where results are known, regardless of the findings	Major congenital malformations
Women who received any first trimester prenatal screening that provides knowledge of pregnancy outcome before enrollment where result is known to be negative	Major congenital malformations
Women with exposure to QUVIVIQ preconception and in each trimester of exposure ^a	Major congenital malformations
Women with exposure to QUVIVIQ preconception and in each trimester of exposure	Minor congenital malformations
Women with exposure to insomnia medications (Cohorts A and B1) by type (continuous vs intermittent), duration, and dosage of exposure	Major congenital malformations
Women in the primary analysis	Spontaneous abortion occurring before 22 weeks of gestation
Women in primary analysis based on gestational age of enrollment	Spontaneous abortion
Women who did not take known teratogens during pregnancy	Major congenital malformations
Women with clinically confirmed insomnia disorder	Major congenital malformations
Women with exposure to QUVIVIQ and additional medications for insomnia treatment from preconception through end of pregnancy	Major congenital malformations

^a The primary cut point will be the date of conception (LMP + 14 days) to the end of the first trimester (14 weeks gestation), additional sensitivity cut points will include 18 weeks prior to conception through the end of the first trimester, conception date to the end of the pregnancy, 18 weeks prior to conception to the end of pregnancy, second trimester exposure only, and third trimester exposure only.

LMP = last menstrual period.

Full details will be described in the SAP.

Confidential

Subgroup analysis

Both Cohort A and Cohort B (overall and separately for Cohorts B1 and B2) will be summarized and compared for primary and secondary outcomes both overall and by the subgroups of the following parameters, if sufficient sample size allows:

- Maternal age category (< 18 years, 18 to < 35 years, 35 to 45 years, and 45 years and older).
- Race/ethnicity.
- Smoking status.
- Other classes of insomnia drugs used during pregnancy and/or during the infants first year of life (among live births).

Additional subgroups of interest may be explored beyond what is outlined above and will be detailed in the SAP.

Analysis of safety outcomes

Interim safety reporting will be conducted every year and will be aligned with the periodic benefit-risk evaluation report reporting schedule. All AE verbatim terms will be recorded and coded using MedDRA version 25.0 or later. All AEs and SAEs collected will be analyzed by preferred terms among prospective pregnancies (overall and within Cohort A, Cohort B1, Cohort B2) and among retrospective pregnancies where applicable.

External comparison

In addition to the internal comparison, results from prospective pregnancies will be descriptively compared to existing data sources or published reports representing the general population with prevalence of birth defects [see Section 5.4.4]. Additional external data sources will be considered if they become available during the study.

5.7.4.5 Case series analysis

Women with retrospective pregnancies who were exposed to QUVIVIQ during pregnancy or within 5 half-lives prior to conception will be included in a separate case series. Analyses in this case series will primarily be qualitative. Pregnancies included in this case series will be described with respect to demographic and clinical information [see Section 5.7.2.1] and QUVIVIQ exposure (e.g., timing of exposure and duration). All reported primary and secondary outcomes will be assessed in this analysis.

5.8 Quality control

5.8.1 Study documentation

The CC PI is responsible for maintaining adequate and accurate records to enable the conduct of the study to be fully documented, including but not limited to the protocol, protocol amendments, ICFs, and documentation of IRB and governmental notification.

Confidential

5.8.2 Coordinating center audits and inspections

The CC inspections may be conducted by Idorsia or an authorized representative for the audit of study data, patients' medical records, and eCRFs.

The CC PI will also permit national and local health authorities to inspect facilities and records relevant to this study.

5.8.3 Retention of records

At the end of the study, the CC PI will receive the data related to patients from their CC in an electronically readable format. Data must be kept at the CC with the study documents. Acknowledgment of receipt of the data is required.

5.9 Limitations of the study methods

Although all possible measures will be taken to ensure the quality and robustness of the data, there are several limitations to the study design to be considered and acknowledged when interpreting the results of this study.

5.9.1 Internal validity of study design

5.9.1.1 Misclassifications

Assessing exposures: Recall of treatment and other potential exposures that could adversely impact the outcome of pregnancy is subject to variability based on the quality of collection by the HCP or the memory of the patient. Where applicable, calendars will be provided to aid the recall of past exposures.

Assessing the primary outcome: A committee of at least 3 qualified, independent teratologists or other appropriate birth defect experts will be used throughout the study to evaluate congenital malformations and other significant findings in Cohort A and Cohort B to ensure proper classification of the primary outcome [Section 10]. The Adjudication Committee will be blinded to QUVIVIQ exposure status to ensure that any misclassification remained after adjudication would be non-differential.

Misclassification of the primary and secondary outcomes remain possible, even with independent review. Where applicable, information provided by the HCP will override the information provided by the patient should there be a discrepancy.

5.9.1.2 Information bias

Patients with prospective pregnancies who have been informed about potential adverse pregnancy outcomes prior to enrollment in the study may exhibit differential recall of their treatment exposures during early pregnancy and may also stop their treatment after learning of the outcome. This study plans to enroll women whose fetal diagnosis has been made prior to enrollment in the registry (whether positive or negative) for major congenital malformations that are unrelated to genetic or aneuploid disorders, and women with or

Confidential

without prenatal testing prior to enrollment that could determine the status of the fetus (e.g., amniocentesis, genetic testing, nuchal translucency screen, chorionic villus sampling, and late-term ultrasound). The differential recall may lead to bias, which will be addressed with the stratification of primary and secondary outcomes by the timing of enrollment with respect to the receipt of prenatal test results. Additionally, the primary analysis will exclude women who have received first trimester prenatal screening in which either aneuploid disorders or genetic disorders that are known to cause major congenital malformations have been detected.

Women with retrospective pregnancies may also have differential recall which may lead to bias and will not be compared to women with prospective pregnancies but will instead be analyzed in a separate case series.

Lastly, as the HCP is not blinded to the exposure status, HCPs may report AEs more frequently in patients exposed to QUVIVIQ than in patients unexposed to QUVIVIQ.

5.9.1.3 Selection bias

Spontaneous abortions most frequently occur in early pregnancy, likely before the pregnancy is recognized. Even if the pregnancy is recognized and confirmed, it is possible that the pregnancy may not be reported to the study if the loss occurred before enrollment in the study. Not capturing all early pregnancy losses will likely lead to an underestimation of the true early pregnancy loss rate. There is no reason to believe that this study will be differentially impacted by this bias, so even though the spontaneous early losses may be underestimated, the relative rate compared with the other registries should not be affected.

There is potential for channeling bias by label indication due to the severity of insomnia and patient insomnia treatment history. Women with more severe insomnia may be more likely to be prescribed QUVIVIQ compared to women with less severe insomnia histories. Baseline insomnia severity and prior treatments will be captured to assess the degree of confounding by indication.

5.9.1.4 Confounding

Covariates collected in both Cohort A and Cohort B include the following: pregnancy follow-up and frequency of mother and infant encounters, medical and medication history (including insomnia treatment), insomnia history, and pregnancy and infant outcomes. Careful selection of variables will be determined as confounding factors known to be associated with adverse pregnancy outcomes (e.g., maternal age, smoking, alcohol consumption, marijuana use, illicit drug use) to examine the distributions between Cohort A and Cohort B. The exploration of insomnia treatment exposures during pregnancy other than QUVIVIQ will also be performed by examining specific drugs and/or drug classes. Sensitivity analyses will complement existing primary analyses in controlling for confounding [see Section 5.7.4.4].

Confidential

